# 9.3 Subject Information and Informed Consent

The ICF will be used to explain the risks and benefits of study participation to the subject in simple terms before the subject will be entered into the study. The ICF contains a statement that the consent is freely given, that the subject is aware of the risks and benefits of entering the study, and that the subject is free to withdraw from the study at any time. Written consent must be given by the subject and/or legal representative, after the receipt of detailed information on the study.

The Investigator is responsible for ensuring that informed consent is obtained from each subject or legal representative and for obtaining the appropriate signatures and dates on the informed consent document prior to the performance of any protocol procedures and prior to the administration of study drug. The Investigator will provide each subject with a copy of the signed and dated consent form.

A separate ICF will be used for subjects who elect to contribute samples for pharmacogenetic analyses.

# 9.4 Subject Data Protection

The ICF will incorporate (or, in some cases, be accompanied by a separate document incorporating) wording that complies with relevant data protection and privacy legislation.

The Sponsor or representative will not provide individual genotype results to subjects, any insurance company, any employer, their family members, general physician or any other third party, unless required to do so by law.

Extra precautions will be taken to preserve confidentiality and prevent genetic data being linked to the identity of the subject. In exceptional circumstances, however, certain individuals might see both the genetic data and the personal identifiers of a subject. For example, in the case of a medical emergency, a Sponsor or representative physician or an Investigator might know a subject's identity and also have access to his or her genetic data. In addition, regulatory authorities may require access to the relevant files.

# **10.0 STUDY ADMINISTRATION**

# **10.1** Administrative Structure

The administrative structure of this study is presented in .

# 10.2 Data Handling and Record Keeping

It is the Investigator's responsibility to maintain essential study documents (protocol and protocol amendments, completed eCRFs, signed ICFs, relevant correspondence, and all other supporting documentation). The study site should plan to retain such documents for approximately 15 years after study completion. The study site should retain such documents until at least two years after the last approval of a marketing application in an ICH region and until there are no pending or contemplated marketing applications in an ICH region or at least two years after the formal discontinuation of clinical development of the investigational product. These documents should be retained for a longer period if required by the applicable regulatory requirements or the hospital, institution, or private practice in which the study is being conducted. Subject identification codes (subject names and corresponding study numbers) will be retained for this same period. These documents may be transferred to another responsible party, acceptable to Sponsor, who agrees to abide by the retention policies. Written notification of transfer must be submitted to Sponsor. The Investigator must contact Sponsor prior to disposing of any study records.

The U.S. Food and Drug Administration (FDA) regulations (21 CFR §312.62[c]) and the ICH Guideline for GCP (see Section 4.9 of the guideline) require that records and documents pertaining to the conduct of this study and the distribution of study drug (including eCRFs, consent forms, laboratory test results, and medication inventory records), must be retained by the Principal Investigator for 15 years after the last marketing application approval in an ICH region or after at least 15 years have elapsed since formal discontinuation of clinical development of the investigational product. The Sponsor will notify the Principal Investigator of these events.

No records should be disposed of without the written approval of the Sponsor.

For studies conducted outside the United States under a U.S. Investigational New Drug (IND) application, the Principal Investigator must comply with U.S. FDA IND regulations and with those of the relevant national and local health authorities.

# **10.3 Direct Access to Source Data/Documents**

The Investigator will prepare and maintain adequate and accurate source documents to record all observations and other pertinent data for each subject randomised into the study.

The Investigator will allow the Sponsor, and authorised regulatory authorities to have direct access to all documents pertaining to the study, including individual subject medical records, as appropriate.

# **10.4** Investigator Information

### **10.4.1** Investigator Obligations

This study will be conducted in accordance with the ICH Harmonised Tripartite Guideline for GCP (GCP, 1997); the U.S. CFR Title 21 parts 50, 56, and 312; and European Legislation; and the ethical principles that have their origin in the Declaration of Helsinki.

The Investigator agrees to conduct the clinical study in compliance with this protocol after the approval of the protocol by the IEC/IRB in compliance with local regulatory requirements. The Investigator and the Sponsor will sign the protocol to confirm this agreement.

### **10.4.2 Protocol Signatures**

After reading the protocol, each Investigator will sign the protocol signature page and send a copy of the signed page to the Sponsor or representative (see the Appendix, Section 12.3). By signing the protocol, the Investigator confirms in writing that he/she has read, understands and will strictly adhere to the study protocol and will conduct the study in accordance with ICH Tripartite Guidelines for GCP and applicable regulatory requirements. The study will not be able to start at any site where the Investigator has not signed the protocol.

### **10.4.3 Publication Policy**

The data generated by this study are confidential information of the Sponsor. The Sponsor will make the results of the study publicly available. The publication policy with respect to the Investigator and study site will be set forth in the Clinical Trial Agreement.

# **10.5** Financing and Insurance

The Sponsor will obtain liability insurance that covers this study as required by local law and/or national regulations and/or ICH guidelines whichever is applicable. The terms of the insurance will be kept in the study files.

# **12.0 APPENDICES**

# 12.1 Sample Crohn's Disease Activity Index (CDAI) Score

	Factor
Number of liquid or soft stools each day for 7 days	×2
Abdominal pain (0-3 on severity) each day for 7 days	×5
Subjective general well-being (0=well to 4=terrible for each day for 7 days	×7
Presence of complications*	×20
Taking diphenoxylate or opiates for diarrhoea	×30
Presence of an abdominal mass (0=none; 2=questionable; 5=definite)	×10
Absolute deviation of haematocrit from 47% in men and 42% in women	×6
Percentage deviation from standard weight	×1

\*One point each is added for each set of complications

- The presence of joint pain (arthralgia) or frank arthritis
- Inflammation of the iris or uveitis
- Presence of erythema nodosum, pyoderma gangrenosum or aphthous ulcers
- Anal fissures, fistulae or abscesses
- Other fistulae
- Fever (> $37.8^{\circ}$ C) during the previous week

Reference: Monteleone, G, Neurath MF, Ardizzone S, Di Sabatino A, Fantini, MC et al. Mongersen, an oral SMAD7 antisense oligonucleotide, and Crohn's disease. N Engl J Med. 2015;372(12):1104-1113.

VHsquared Ltd Protocol V56502 Drug Name: V565

# 12.4 Protocol Amendment 1.3 Summary of Changes

The following non-substantial changes were implemented with Protocol Version 1.3:

- 1. Inclusion criterion 11(vii) amended to include reference to Section 6.2.2.
- 2. Section 6.2.2 additional detail provided for vasectomised partners and detailed definition of sexual abstinence.
- 3. Table 2: Activated partial thromboplastin time added to Safety Assessments.
- 4. Table 4: Activated partial thromboplastin time added to Additional Tests (Screening Only).

### **MODIFICATION HISTORY**

Unique Identifier for this Version	Date of the Document Version	Author	Significant Changes from Previous Authorized Version
V1.0	12MAR2019		Not Applicable – First Version

Page 4 of 40

### **1. INTRODUCTION**

This document describes the rules and conventions to be used in the presentation and analysis of efficacy, pharmacokinetics (PK) and safety data for Protocol V56502. It describes the data to be summarised and analysed, including specifics of the statistical analyses to be performed.

This statistical analysis plan (SAP) is based on protocol version 1.3, dated 24 August 2016 and amendment 02 December 2016.

### 2. STUDY OBJECTIVES

### **2.1. PRIMARY OBJECTIVE**

The primary objective is

• To evaluate the efficacy of V565 555 mg three times a day (TID) in subjects with active Crohn's disease (CD) measured by the proportion of subjects achieving response to therapy. Response is defined as reduction in the Crohn's Disease Activity Index (CDAI) scores and in inflammatory markers C-reactive protein [CRP] or faecal calprotectin [FCP] at Day 42.

### **2.2. SECONDARY OBJECTIVES**

The secondary objectives are

- To further characterise the efficacy of V565 in subjects with active CD assessed by changes in CDAI scores and/or inflammatory markers
- To assess the effects of V565 based on changes in Abdominal Pain and Stool Frequency instrument (PRO-2) scores
- To assess safety and tolerability of V565

### **2.3.** PHARMACOKINETIC OBJECTIVES

The pharmacokinetic (PK) objective is

• To determine the concentration of V565 in serum and urine

STATISTICAL ANALYSIS PLAN: PROTOCOL V56502 Page 10 of 40

### **2.4.** EXPLORATORY OBJECTIVES

The exploratory objectives are

- To assess the proportion of subjects achieving CRP or FCP levels within normal limits
- To assess changes in CDAI scores and CRP or FCP levels over time
- To determine changes in anti-V565 antibody titre
- •

### **2.5.** EXPLORATORY ENDOSCOPY SUBSTUDY OBJECTIVES

• To investigate the effect of V565 on changes in endoscopic mucosal appearance, evaluated with an overall assessment and the Simple Endoscopic Score for Crohn's Disease (SES-CD), as determined by a central reader

### **3. STUDY DESIGN**

### **3.1. GENERAL DESCRIPTION**

This study will be a multiple-site, double-blind, placebo-controlled, parallel-group proof-of-concept study in approximately 126 subjects with active CD. This study will include subjects who have a confirmed diagnosis of CD for at least three months and have CD involving the ileum and/or colon.

The duration of treatment will be 42 days (six weeks); each subject's participation in the study will be approximately 12 weeks. This includes a screening period of up to 28 days, a treatment period of 42 days and a follow-up period of 14 days after the last dose of study drug.

Subjects will be randomised into one of two treatment arms: either V565 or placebo using a 2:1 active:placebo ratio. Randomisation will be stratified to ensure treatment groups have similar rates of prior anti-tumour necrosis factor alpha ( $TNF\alpha$ ) therapy.

Subjects will receive three V565 185 mg capsules three times daily or matching placebo, for 42 days (six weeks). The total daily V565 dose is 1665 mg.

😵 VHsquared

STATISTICAL ANALYSIS PLAN: PROTOCOL V56502 Page 11 of 40

Figure 1: Study Diagram

- a. Screening may be a maximum of 28 days but may be shorter depending on the amount of time required to determine that a subject is eligible for the study based on all inclusion/exclusion criteria, including laboratory values, CDAI score, CRP (or FCP) level and results of the ileocolonoscopy.
- b. All eligible subjects will have an ileocolonoscopy at Visit 2. The timing of Visit 2 is flexible, but must not occur until the subject has been declared eligible with regard to CDAI scores and CRP (or FCP) levels. The ileocolonoscopy must occur prior to Day 1.
- c. Subjects will enter an exploratory endoscopy substudy if the subject's baseline SES-CD score is ≥7 (if ileum and colon involved) or ≥4 (if the lesions are confined to the ileum).
- d. Subjects may not be randomised unless the ileocolonoscopy at Visit 2 indicates the presence of active disease.
  e. Subjects in the exploratory endoscopy substudy will have a post-treatment ileocolonoscopy scheduled for Day 42.

CDAI: Crohn's Disease Activity Index; CRP: C-reactive protein; FCP: Faecal calprotectin; R: Randomisation; SES-CD: Simple Endoscopic Score for Crohn's Disease

### **3.2.** SCHEDULE OF EVENTS

Schedule of events can be found in Table 2 of the protocol.

### **3.3.** CHANGES TO ANALYSIS FROM PROTOCOL

In the protocol section 8.2.1 it is mentioned that the baseline CRP and baseline FCP results will be included as covariates in the statistical model for logistic regression. CRP or FCP will be used to determine inflammation status at baseline. Some subjects may appear 'normal' on the basis of their CRP result however the FCP measurement reveals the presence of inflammation. As FCP will be measured for subjects only if CRP is <5 mg/L, FCP will be missing for many subjects. In addition, the CRP result for subjects who entered on the basis of inflammation measured by a FCP result => 250 ug/g will not be meaningful as a reflection of inflammation status. For these reasons neither FCP nor CRP will be incorporated into the primary model fit. However, if a subject is enrolled in the study based on the baseline result of FCP the definition of response will incorporate a 40% reduction in CRP. If a subject is enrolled in the study based on the baseline result of FCP the definition of response will incorporate a 40% reduction in CRP.

STATISTICAL ANALYSIS PLAN: PROTOCOL V56502 Page 12 of 40

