In an exploratory endoscopy substudy, subjects with more severe disease at the Visit 2 ileocolonoscopy (a SES-CD  $\geq$ 7, if ileum and colon are involved or  $\geq$ 4 if only the ileum is involved) will undergo a second ileocolonoscopy at the end of treatment (Day 42) to evaluate changes in the mucosa.

Pharmacokinetic (PK) evaluations will be based on concentrations of V565 measured in serum and urine. Safety will be assessed through evaluations of adverse events (AEs), clinical laboratory results, vital signs, physical examinations, electrocardiograms (ECGs) and concomitant medications.

Planned number of subjects:	Approximately 126 randomised to receive study drug in a
3	2:1 active:placebo ratio (84:42)
	Approximately 114 to complete (76:38) based on an estimated dropout
	rate of 10% during treatment

Diagnosis and main criteria for inclusion:	This study will enrol adult subjects with active CD. The main criteria for inclusion are:
	
 
History of CD (confirmed by ileocolonoscopy) of at least three months duration prior to Visit 1
 
CDAI score of ≥220 to ≤450 during Screening
 
CRP ≥5 mg/L (or, if CRP is normal, FCP ≥250 µg/g) at Screening
 
Active CD of ileum and/or colon as determined by the baseline ileocolonoscopy
 
Female subjects must not be pregnant and male and female subjects must agree to use effective contraception throughout the study and for 90 days after the last dose of study drug.
 
Subject must have failed or experienced intolerance to at least one of the following: aminosalicylates, corticosteroids; immunosuppressants (e.g., azathioprine [AZA], 6-mercaptopurine [6-MP], or methotrexate [MTX]).
 

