#### Efficacy

The primary endpoint will be analysed using a logistic regression model with treatment as the fixed effect and prior anti-TNF $\alpha$  therapy, baseline CDAI score, baseline CRP and baseline FCP values as covariates. For the active treatment versus placebo comparison, the results will be presented in terms of an odds ratio together with its associated 95% confidence interval (CI) and 2-sided p-value. Two-sided 95% CIs for the odds ratio will be provided.

Unless otherwise specified, the proportions of subjects fulfilling the relevant requirements will be presented with 95% CIs for all the primary and secondary endpoints.

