# 5.6 Method of Assigning Subjects to Treatment Group

Once the subject provides an informed consent and meets inclusion and exclusion criteria, the study site will request the study drug assignment using the Interactive Web Activated Response System (IWRS). Approximately 126 subjects will be randomised in a 2:1 ratio (84 subjects in the V565 arm and 42 subjects in the placebo arm). Randomisation will be stratified to ensure treatment groups have similar rates of prior anti-TNF $\alpha$  therapy.

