### **6.6. S**TATISTICAL TESTS

The default significance level will be (5%); confidence intervals will be 95% and all tests will be two-sided, unless otherwise specified in the description of the analyses.

Two-sided CIs will be assessed at the 5% significance and two-sided p-value will be reported.

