### **10.** DEMOGRAPHIC AND OTHER BASELINE CHARACTERISTICS

Demographic data and other baseline characteristics will be presented for the ITT, SAF and PP populations.

No statistical testing is planned for demographic or other baseline characteristics.

Summaries for continuous and categorical variables (as described in section 6) will be presented for each treatment and Total.

Demographics and baseline characteristics will be presented in a listing by subject.

The following demographic and other baseline characteristics will be reported for this study

- Age (years) at screening as collected from eCRF
- Sex
- Race
- Ethnicity
- Body Weight (kg) at screening
- Height (cm) at screening as collected from eCRF
- BMI (kg/m^2) at screening as collected from eCRF
- Prior Anti-TNF Therapy
- Childbearing potential for female subjects
- Disease duration (months)
- Baseline CDAI score
- Baseline CRP for patients qualifying on CRP
- Baseline FCP for patients qualifying on FCP
- Baseline SES-CD score
- Prior CD medication use

STATISTICAL ANALYSIS PLAN: PROTOCOL V56502 Page 20 of 40

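### SAP 3.3 drops the baseline inflammatory marker from the primary model, although coding it by qualifying marker would meet both stated reasons and recover the intent of the planned adjustment

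*SAP*

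**What the plan says.** The Efficacy part of the protocol synopsis specifies a logistic model with treatment, prior anti-TNFα therapy and "baseline CDAI score, baseline CRP and baseline FCP values as covariates".

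SAP 3.3 declares a change: "For these reasons neither FCP nor CRP will be incorporated into the primary model fit". It explains that FCP is measured only when CRP is below 5 mg/L, so it will be missing for many subjects, and that CRP does not reflect inflammation in those who entered on FCP. SAP 7.1 and 15.1.3 therefore keep only treatment, prior anti-TNFα therapy and baseline CDAI. The sensitivity analyses in SAP 15.1.4 repeat that model with other imputations and on the PP population. No other coding of the marker is discussed.

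Three other passages bear on this:

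- Entry requires CRP of at least 5 mg/L or, if CRP is normal, FCP of at least 250 µg/g (Protocol 4.4.1 and 6.1.3).
- SAP 10 already tabulates "Baseline CRP for patients qualifying on CRP", and the FCP counterpart.
- SAP 15.1.1 requires a fall of at least 40% from the baseline value of one marker, chosen by baseline CRP status.

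**The concern.** The reasons given rule out one particular coding, not adjustment as such. By the entry criteria an eligible subject has a qualifying marker, and SAP 10 already holds its baseline value by entry route.

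The marker is also a plausible predictor of the endpoint. Response includes a percentage fall from that same baseline value, and a value that is high by chance tends to fall on repeat measurement. Marker type may matter too, because it decides which assay judges response. Randomisation is stratified only on prior anti-TNFα therapy (Protocol 5.6), so neither the type nor the level of the marker is balanced by design, and no planned analysis adjusts for them. At stake are some power and protection against chance imbalance in a trial of about 126 subjects.

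**Working it through.** **The plan's own figures.** Protocol 5.6 gives 84:42. The synopsis gives "Approximately 114 to complete (76:38) based on an estimated dropout" "rate of 10% during treatment". Check: 126 × 0.9 = 113.4; by arm, 84 × 0.9 = 75.6 and 42 × 0.9 = 37.8, which round to 76 and 38. In reverse, 114 / 0.9 = 126.7. The figures agree to rounding. The available text gives no response rates or power, so the planned power cannot be reproduced. At 84:42, two-sided 5% and 80% power, the detectable V565 rate is 38.6% against 15% on placebo, 44.8% against 20%, and 56.0% against 30%. The rates assumed below are close to these.

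**Is the SAP right that the literal protocol model fails?** Yes. With CRP and FCP both entered, a complete-case fit keeps only FCP entrants. If they are 10, 20, 30 or 50% of 126 (assumed), that leaves about 13, 25, 38 or 63 subjects.

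**Does coding by qualifying marker answer both reasons?**

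- *FCP missing by design:* CRP entrants contribute CRP and FCP entrants contribute FCP, so the structural gap disappears.
- *CRP uninformative in FCP entrants:* CRP is never used as their marker value.

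**Chance imbalance in marker type.** The 95% range of the difference between arms in the FCP-entrant share p is ±1.96 × √[p(1 − p)(1/84 + 1/42)]. For p = 0.3 this is 1.96 × √(0.21 × 0.0357) = 0.170, or ±17 points. It is ±11 points at p = 0.1 and ±19 at p = 0.5. If response differs by 5 to 20 points between marker types (assumed), an imbalance at the 17-point limit shifts the crude arm difference by 0.17 × 5 = 0.9 to 0.17 × 20 = 3.4 points.

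**Power.** Simulated logistic regression, 84:42, 4,000 trials per setting, two-sided 5% Wald test. Assumed: 30% FCP entrants, 30% prior anti-TNFα use with no effect on response, a CDAI odds ratio of about 1.35 per SD, no effect of marker type itself, and no missing data. The two-term model adds the marker indicator and the baseline marker value standardised within type, with a common slope.

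| Response, placebo v V565 | Marker OR per SD | SAP model | Two-term model | Change (points) |
|---|---|---|---|---|
| 20% v 45% | 1.0 | 80.4% | 80.2% | -0.2 |
| | 1.5 | 81.2% | 82.6% | +1.4 |
| | 2.0 | 80.8% | 84.2% | +3.4 |
| | 3.0 | 81.9% | 88.1% | +6.2 |
| 30% v 56% | 1.0 | 80.5% | 80.6% | +0.1 |
| | 1.5 | 80.9% | 81.9% | +1.0 |
| | 2.0 | 81.9% | 84.6% | +2.7 |
| | 3.0 | 79.9% | 86.7% | +6.8 |
| 15% v 38% | 1.0 | 79.2% | 78.7% | -0.5 |
| | 1.5 | 78.3% | 79.2% | +0.9 |
| | 2.0 | 78.5% | 82.1% | +3.6 |
| | 3.0 | 77.0% | 84.6% | +7.6 |

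Separate slopes for CRP and FCP (three terms) gave practically the same power; the largest loss was 0.6 points (80.4% to 79.8%, and 79.2% to 78.6%). The paired simulation error of such changes is about 0.3 to 0.4 points.

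**Type I error** (20% or 30% response in both arms): 4.2 to 5.2% for the SAP model, 4.2 to 5.3% with two terms and 4.4 to 5.4% with three.

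**The case against.** The strongest reply is that the SAP contains no error here. The change is declared and its reasons are correct as far as they go. The reduced model keeps the stratification factor and baseline CDAI, and it holds its type I error. That stands. A reader might infer that dropping the marker biases or invalidates the primary analysis; neither the documents nor the calculations support that.

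Four other tempting claims also go too far:

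- *Adjustment can only help.* With a non-prognostic marker the simulated change was about zero, with losses of up to 0.6 points. The documents do not say how prognostic the marker is.
- *Adjustment buys precision.* In logistic regression the standard error of the treatment log odds ratio rises. In six settings with the marker coded as the log ratio to its entry threshold it rose every time, for example from 0.457 to 0.465 and from 0.436 to 0.468. The power gain arises because the conditional odds ratio lies further from 1. At 20% v 45% and a marker odds ratio of 2, the median log odds ratio went from 1.23 to 1.39 with separate slopes. The two odds ratios are not directly comparable.
- *The coded covariate has no missing data.* The primary analysis includes all randomised subjects (SAP 5.1), and SAP 5.2 foresees violations of the CRP/FCP criterion. Also, baseline is the last value before Day 1 (SAP 6.2), while on-treatment FCP is measured only if screening CRP was below 5 mg/L (Protocol 6.1.3). A CRP entrant whose later pre-dose CRP is below 5 mg/L may have no FCP value and so fit neither branch of SAP 15.1.1.
- *The same case holds for every responder endpoint.* Three of the four secondary responder endpoints use CDAI alone (Protocol 8.2.2), so the link to the marker component does not apply to them.

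These limits narrow the proposal but do not defeat it.

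**Conclusion.** The point holds as an inexpensive improvement, not as a correction of an invalid analysis. The reasons in SAP 3.3 justify dropping two separate covariates; they do not justify dropping the marker. Coding by qualifying marker recovers the intent of the protocol's adjustment, though not its literal model.

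The expected gain is about 0 (at worst about -0.6 points of power) if the marker is not prognostic, about +1 point at an odds ratio of 1.5 per SD, about +3 at 2, and +6 to +7.5 at 3. Type I error stays near 5% either way. All of this rests on assumed response rates, FCP share and prognostic strength. The simulation also gave marker type no effect of its own, so it credits nothing to adjustment for that imbalance.

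**What to change.** Before unblinding, amend SAP 3.3, 7.1 and 15.1.3:

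1. Add an indicator of qualifying marker (CRP or FCP), fixed from the screening result on which eligibility was decided.
2. Add the log baseline value of that marker, standardised within marker type. Standardising avoids assuming that a log unit of CRP and a log unit of FCP have the same effect.
3. State a rule that keeps every ITT subject in the model. For example, assign the marker by screening CRP below 5 mg/L or at least 5 mg/L, and give a missing value the within-marker mean (0 on the standardised scale).
4. Use this model for the primary endpoint and for the secondary endpoint combining CDAI and marker reduction. It is optional for the CDAI-only endpoints. Protocol 8.2.2 ties them to the primary model, so the SAP should say which model applies.
5. Keep the current model as a sensitivity analysis, noting that its odds ratio is not directly comparable.
6. Reconcile SAP 3.3, which judges FCP entrants on a CRP reduction (the sentence is printed twice), with SAP 15.1.1, which judges them on FCP, so that covariate and response use the same marker. In the same edit, correct the CRP unit: 15.1.1 prints mg/dL where the entry criteria use mg/L, a tenfold difference.

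The cost is SAP wording and two parameters, with roughly 38 to 60 responders expected under the assumed rates, plus a slightly larger standard error. After unblinding, the adjusted model could only be a labelled post hoc analysis.

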### 6.1.3 Biomarkers of Inflammation

The collection of CRP and/or FCP will occur at the time points indicated in .

C-reactive protein is an acute-phase reactant produced in the liver and is an easily measured non-specific marker of inflammation. It is a widely used marker of inflammation in CD and elevations in CRP have been associated with endoscopic inflammation in CD [15, 16].

C-reactive protein will be analysed in blood samples. If CRP values are normal, FCP will be assessed in the faecal samples. FCP will be used as the eligibility test if CRP results are <5 mg/L. During the treatment and follow up phase of the study, FCP will only be evaluated in subjects whose screening CRP was <5 mg/L, and who qualified for the study based on their screening FCP value.

Calprotectin is abundant in the cytosol of activated neutrophils. The amount of FCP is directly proportional to neutrophil influx into the intestinal tract and is a reliable non-specific marker of intestinal inflammation [17, 18, 19]. While currently endoscopy with biopsy is considered the gold standard for evaluating the extent and location of inflammatory mucosal lesions, studies have shown that FCP may also be a useful marker of intestinal inflammation.

On Day 1, the faecal sample for FCP should be collected prior to administration of the first dose of study drug. The subject may also provide a sample from faeces passed one day prior to the scheduled visits. These samples will be collected in sterile containers (to be provided to the subjects) and refrigerated at home. At each sampling time point, approximately 2 g to 5 g of faeces will be collected.

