#### 15. **EFFICACY OUTCOMES**

#### 15.1. **PRIMARY EFFICACY**

#### 15.1.1. **PRIMARY EFFICACY VARIABLE & DERIVATIONS**

The primary efficacy variable is Responders at Day 42

A Responder is defined as subjects achieving both CDAI ≥70-point reduction from Baseline OR CDAI score <150, and a reduction of  $\geq$ 40% from the baseline value of CRP (where CRP at baseline => 5mg/dL) or FCP (where CRP at baseline <5mg/dL and FCP at baseline =>250 ug/g)

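### SAP 3.3 twice judges FCP-enrolled subjects on a 40% fall in CRP, contradicting both its own reasoning and the responder derivation in SAP 15.1.1

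*SAP*

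**What the plan says.** SAP 3.3 (Changes to Analysis from Protocol) explains why baseline CRP and FCP leave the logistic model. One reason is availability: "As FCP will be measured for subjects only if CRP is <5 mg/L, FCP will be missing for many subjects". The other is that CRP in subjects who entered on FCP "will not be meaningful as a reflection of inflammation status".

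The paragraph then turns to the responder definition. It begins "However, if a subject is enrolled in the study based on the baseline result of FCP the definition of response will incorporate a 40% reduction", and the marker named is CRP. The following sentence repeats the condition and the marker: "enrolled in the study based on the baseline result of FCP the definition of response will incorporate a 40% reduction in CRP". Neither sentence gives a rule for subjects enrolled on CRP, and neither assigns FCP to anyone.

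SAP 15.1.1 (Primary Efficacy Variable & Derivations) gives a different rule. The 40% reduction is taken "from the baseline value of CRP (where CRP at baseline => 5mg/dL") or, otherwise, from "FCP (where CRP at baseline <5mg/dL and FCP at baseline =>250 ug/g").

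Protocol 6.1.3 says that during treatment and follow-up "FCP will only be evaluated in subjects whose screening CRP was <5 mg/L" and who qualified on their screening FCP. Protocol 8.2.1 refers only to CRP or FCP and does not say which marker applies to whom.

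**The concern.** The responder definition is the primary endpoint. For subjects who qualified on FCP, 3.3 and 15.1.1 name different markers, so two programmers working from the same SAP could produce different primary results.

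If 3.3 were followed, the damage would run in one direction. These subjects enter with CRP below 5 mg/L, so there is little for the drug to lower, and a 40% fall is largely measurement and biological variation. Subjects whose FCP fell would be counted as failures, and chance dips in CRP would be counted as marker successes in either arm. Both effects pull the treatment difference towards zero. If the conflict were noticed only after unblinding, either choice of rule would be open to challenge.

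**Working it through.** **1. The texts side by side**

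| Subject enters on | SAP 3.3 | SAP 15.1.1 | On-treatment data (Protocol 6.1.3) |
|---|---|---|---|
| CRP | no rule given | CRP | CRP; FCP not followed |
| FCP | CRP (stated twice) | FCP | FCP followed |

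In the FCP row, 3.3 and 15.1.1 cannot both hold. The protocol's sampling scheme supports 15.1.1. So does 3.3's own statement about CRP in these subjects.

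**2. Whether 15.1.1 can serve as the reference as printed**

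It gives the CRP cut-off in mg/dL. Since 5 mg/dL = 5 × 10 = 50 mg/L, this is ten times the 5 mg/L used in 3.3 and in the protocol. Read literally, a subject with CRP from 5 to below 50 mg/L and no FCP result fits neither branch. Both statements of the rule therefore need correction.

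**3. Illustrative size if 3.3 were implemented**

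The available text gives no assumed response rates or power, so there is no plan figure to reproduce.

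From the documents: 84 V565 and 42 placebo subjects (Protocol 5.6), two-sided 5% test (Protocol 8.2).

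Assumed:
- within-subject SD of log CRP, s = 0.35 to 0.6;
- intended response 45% against 20%, whichever the route of entry;
- CDAI response 60% against 40%;
- CRP falls independent of CDAI response, with no drug effect on a normal CRP;
- share entering on FCP, f = 20% to 40%.

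Chance of a fall of at least 40% between two measurements: q = Φ(ln 0.6 / (s√2)), with ln 0.6 = −0.511.
- s = 0.35: Φ(−1.032) = 15.1%
- s = 0.5: Φ(−0.722) = 23.5%
- s = 0.6: Φ(−0.602) = 27.4%

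Response among FCP-enrolled subjects under 3.3 is 0.60q against 0.40q.
- s = 0.35: 9.1% against 6.0%, a difference of 3 points
- s = 0.6: 16.4% against 10.9%, a difference of 5 points

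Overall rates are (1−f) × 45% + f × 0.60q against (1−f) × 20% + f × 0.40q.

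Power = Φ[(d − 1.96·SE₀)/SE₁], with SE₀ pooled and SE₁ unpooled. With no FCP problem:
- pooled rate = (42 × 0.20 + 84 × 0.45)/126 = 0.367
- SE₀ = 0.0911, SE₁ = 0.0822
- power = Φ[(0.25 − 0.1785)/0.0822] = Φ(0.870) = 81%

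| s | f | V565 | Placebo | Difference (points) | Power |
|---|---|---|---|---|---|
| – | 0 | 45.0% | 20.0% | 25.0 | 81% |
| 0.35 | 20% | 37.8% | 17.2% | 20.6 | 67% |
| 0.6 | 20% | 39.3% | 18.2% | 21.1 | 68% |
| 0.35 | 40% | 30.6% | 14.4% | 16.2 | 51% |
| 0.6 | 40% | 33.6% | 16.4% | 17.2 | 53% |

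At f = 10%, power is 74–75%.

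**4. A second, simpler model**

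Start from 80% power at 84:42 (20% against 44.8%, or 30% against 56.0%) and assume no treatment effect at all on response in FCP-enrolled subjects. The difference is multiplied by (1−f): for the first pair at f = 20%, 24.8 × 0.8 = 19.8 points. Power is 71–72%, about 61%, 50–51% and 39–40% for f = 10%, 20%, 30% and 40%.

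**The case against.** The best defence is that this is a copying slip, not a chosen rule. Two nearly identical sentences in a row suggest that one was meant to pair CRP entry with CRP and the other FCP entry with FCP. The section devoted to the derivation gets the pairing right, the sampling scheme fits it, and SAP section 10 tabulates baseline FCP for those qualifying on FCP. On this view nobody would program 3.3, and the power loss is hypothetical. Much of this stands. The intent is very probably as described, and the loss arises only if 3.3 is followed. But the intent is an inference, no visible text gives 15.1.1 precedence, and 3.3 is the section that formally records departures from the protocol.

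The figures rest on rates, variability and FCP shares that are not in the documents. That is correct. They show scale only, and the contradiction does not depend on them.

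Section 15.1.1 routes by baseline values, whereas 3.3 speaks of enrolment, so the two could part if an unscheduled value crossed the threshold. The gap is negligible: baseline for CRP and FCP is the last value before Day 1 (SAP 6.2), and a retest replaces the original value for eligibility (Protocol 4.2.1).

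Parts of SAP 15.1 and 15.2 are missing from the public copy and may hold further routing text. That would not remove the two sentences in 3.3.

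**Conclusion.** The concern holds. SAP 3.3 states twice, in complete sentences, a marker rule for FCP-enrolled subjects that contradicts 15.1.1 and its own preceding argument. A probable slip in a live rule for the primary endpoint still has to be corrected before unblinding, because following it would misclassify the FCP-qualified subgroup.

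If 3.3 were implemented, the treatment difference among FCP-enrolled subjects would fall from an assumed 25 points to about 3–5. With 20–40% of subjects entering on FCP, the overall difference would be about 16–21 points and power about 51–68%, against 81%. The simpler model gives 61% down to 39–40% over the same shares. All of these depend on the stated assumptions. If 15.1.1 is what gets programmed, with its units put right, there is no loss.

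**What to change.** Replace the two sentences in SAP 3.3 with one rule per route: subjects who qualified on CRP need a fall of at least 40% in CRP, and subjects who qualified on FCP need a fall of at least 40% in FCP.

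State that 15.1.1 is the operative derivation, and correct its CRP cut-off from mg/dL to mg/L. Add a sentence fixing the route by the value on which the subject finally qualified, so that 3.3 and 15.1.1 cannot diverge.

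Apply the same routing to the secondary composite in SAP 15.2.1 (100-point CDAI fall with a 50% marker fall), where the visible text does not say which marker applies to whom.

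The cost is a SAP text correction, with a matching check of the programming specification, before unblinding. No new data are needed.
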